8.3.3 Database Access

Access to the database is granted to personnel based on specific security roles associated with particular privileges related to the role they have in the study. Access levels and their associated privileges are defined in the finalized Data Management Plan, and user access will be administered via the Emergent Data Management System Administrator.

- Data Management privileges include access to view data, generate and manage queries, lock and unlock eCRF pages, generate listings and create reports (including ad-hoc reporting).
- Clinical Monitor privileges include access to generate and manage queries, generate listings, run reports and to mark pages as source document verified. Access to add/change data is limited to study site personnel.
- Study Coordinator privileges are limited to data entry, report generation and query resolution.
- Principal Investigator privileges are limited to applying a signature to the data as well as read-only access to all of the eCRFs.

8.3.4 Database Security

Emergent Data Management system administrator controls user access per user roles and privileges. Only qualified study personnel will be granted database access. Password is required for user access. Password must have minimum of ten characters, must contain at least three of the following four items:

- contains one or more uppercase letters
- contains one or more lowercase letters
- contains one or more numbers
- contains one or more special characters

Passwords expire after 90 days. To reset the password, the user will need to provide the old password and correct answers to security questions in the user profile.

8.3.5 Database Locking

The database is locked when all expected data are entered, monitored, cleaned (known discrepancies resolved) and signed by the PI. See Section 8.3.2 and 8.5.

8.3.6 Database Back-up

Disaster mitigation measures are as follows:

- All data is encrypted and transferred nightly to Medrio's hosting provider servers
- All backups are stored on secure network based file storage on machines separate from the server being backed up
- All electronically stored Corporate Data is backed up nightly

- Full backups are taken every night and stored in a secure facility separate from the production environment
- Incremental backups occur every 15 minutes to a secure facility that is separate from the production environment.

If a device containing study data is lost or stolen, the loss will be reported through the respective installation's chain of command within 24 hours of the event's discovery, if occurring on a weekday, or within 24 hours of the next business day. The loss will also be reported to the study sponsor within the same 24 hour interval.

8.4 Retention of Study Documentation

The Investigator will maintain all study documentation, including copies of ICFs, eCRFs, and documentation of study vaccine accountability for either 2 years following FDA or other regulatory approval of PXVX0317, or 2 years after clinical development of PXVX0317 is discontinued, unless a longer period is required by applicable law or regulation. The Investigator will destroy study documentation only upon instruction by the Sponsor and must notify the Sponsor upon completion of such destruction.

All paper source document data including the entire regulatory study file will be stored and disposed of in accordance with WRAIR CTC SOP XXXXXXXXXX *Establishment and Maintenance of a Regulatory Document File.*

Electronic data will be stored by the sponsor and disposed of in accordance with EBSI SOPs.

8.5 Data Monitoring

The Sponsor or designee will monitor completed eCRFs against source documentation at regular intervals throughout the study to verify adherence to the protocol; completeness, accuracy, and consistency of the data; and adherence to local regulations on the conduct of clinical research. The Investigator must make source documentation accessible to the Sponsor or designee as needed to verify the information in the eCRFs. The Investigator agrees to cooperate with the Sponsor or designee to ensure that any problems detected in the course of data monitoring are resolved.

An audit trail will capture a history of all data entry transactions and query responses, notes, author(s), and date/time stamps based on the server time. Any changes including reason for change will be electronically captured for each question in the eCRFs. System validation, recovery, security, and compliance were documented.

The DM/Designee will periodically run reports to facilitate data cleaning and to provide progress reports at project meetings as needed.

The DM/Designee will work with the SAS programmer(s) and the statisticians to provide data listings and/or snapshots for SAE reconciliation, laboratory data reconciliation, Safety reporting, FDA IND Annual Report and other data reviews and/or reports if applicable as needed.

8.6 Laboratory Data

This study will employ electronic transfers of laboratory data generated from clinical specimens collected by the Investigator. The Investigator is responsible for the adequacy and accuracy of data associated with collection of these specimens. The Sponsor is responsible for the adequacy and accuracy of the data generated by external laboratories.

8.7 Audit Compliance

The Investigator must permit the Sponsor and/or designee, regulatory agencies, the WRAIR IRB, and the USAMRIID Office of Human Research Oversight direct access to facilities and study documentation for the purpose of auditing study conduct. Direct access includes examining, analyzing, verifying, and reproducing any records and reports that are needed for the evaluation of the study.

9 STATISTICAL ANALYSIS

9.1 Sample Size Calculation

The sample size here was chosen based on the number of subjects in the Fort Detrick Special Immunization/Special Procedures Program (USAMRIID) who are available for screening. Of the approximately 60 available, 30 are expected to enroll in this trial along with an equal number of alphavirus naïve age- and gender-matched subjects. Based on an interim analysis of this vaccine lot and regimen in Study PXVX0317-001, at least 95% of the alphavirus-naïve controls are expected to seroconvert in this trial. Assuming that the alphavirus-naïve group has a 95% seroconversion rate, a total sample size of 60 subjects affords 80% power to detect a significant difference between groups if the seroconversion rate in the prior alphavirus vaccine recipients is 65% or less. Or, in other words, power is 80% to detect a difference between groups if the seroconversion rate in the prior alphavirus recipients is 30 percentage points lower than in the alphavirus-naïve group. Compared to the previously cited studies in which decrements in the proportion of seroconversion of 64% (McClain 1998) and 100% (Harrison 1971) (DeMeio 1979) were seen, this study is adequately powered to detect immune interference on the order of one-half to one-third of what has previously been described.

In the event that we have overestimated the willingness of this pool of eligible subjects to participate, the ability to detect differences in the proportion of seroconversion of the same order as was previously shown by McClain (36% versus 95% seroconversion), 10 subjects per group would afford 71% power to detect a significant difference. The power of other combinations of seroconversion rate and sample size can be seen in Table 3. For example, 10 subjects per group afford 81% power to detect a difference between groups if the seroconversion rate is as low as 30% in the prior alphavirus vaccine recipients, while 20 subjects per group provide 89% power to detect a difference if the seroconversion rate is 50% or lower among prior alphavirus recipients. This is certainly less than ideal in terms of designing a field study in an area endemic for other alphaviruses. The decision to conduct such a study will be dependent on many factors and the residual possibility that a lesser degree of immune interference may have gone undetected will have to be considered. If, on the other hand, immune interference on the order of that reported by DeMeio is seen in which a neutralizing antibody response is entirely abrogated, data from this study would be sufficiently compelling to avoid recruiting for field studies in areas co-endemic for other alphaviruses.

Table 3: Power of Detecting a Significant Difference between Prior Alphavirus Vaccine Recipients and Alphavirus-naïve Vaccine Recipients with a 95% Seroconversion Rate

Number of Subjects per Arm	Seroconversion Rate among Prior Alphavirus Vaccine Recipients				
	30%	40%	50%	60%	70%
10	81%	63%	43%	24%	9%
20	> 99%	97%	89%	72%	45%
30	> 99%	> 99%	98%	89%	63%

Power of each combination estimated from a Fisher's exact test comparing the seroconversion rate observed among prior alphavirus vaccine recipients to the rate observed among alphavirus-naïve vaccine recipients assuming the true rate in the latter group is 95%.

With respect to safety as a study endpoint, this study will have 80% power to detect a 30% difference between pre-exposure groups in the incidence of any single or aggregate solicited adverse event expected to occur in 5% of the subjects in one of the groups. With a total of 60 subjects receiving PXVX0317, there is a 95% chance that an uncommon AE – one expected to occur in 5% of vaccinees – will be observed at least once in the trial.

9.2 Treatment Period

The treatment and observation period begins at the time of vaccine administration and extends through the Day 29 visit. The follow-up period spans the time following the Day 29 visit through the end-of-study visit on Day 182 (± 14).

9.3 Treatment Groups

Subjects will all receive the same vaccine regimen in an open label fashion. There will be no randomization and no blinding as the primary endpoint (immune response at Day 22) is not subject to subjective interpretation. The participants themselves already know whether or not they have previously received another alphavirus vaccine as such vaccines have only been available through IND and their administration required informed consent. The safety profile of this vaccine is well-established for a phase 2 candidate and is not expected to differ between the two groups enough to justify the inclusion of a placebo group. Laboratory workers at USAMRIID have been exposed to multiple alphavirus and other vaccines in the past without evidence of any clinically significant adverse health effects ([Pittman 2004](#)).

Subject matching will be done by age (± 3 years) and gender, both of which have been shown to play roles in vaccine immunogenicity in general ([Klein 2016](#)) and alphavirus immune interference in particular ([Reisler 2012](#)), ([Pittman 2009](#)).

9.4 Populations for Analysis

Study Population: All screened subjects who provide informed consent and provide demographic and other baseline screening measurements, and are assigned a study subject ID.

Exposed Population: All subjects in the Study Population who receive study vaccination.

Safety Population: All subjects in the Exposed Population who provide safety assessment data. This generally includes anyone who was not lost to follow-up at Day 1 as they will be at risk for reporting an SAE.

Immunogenicity Evaluable Population (IEP): The IEP includes all subjects in the Exposed Population who:

- Have no important protocol deviation or other reason to be excluded as defined prior to database lock.
- Have not received a prohibited medication.
- Provide evaluable serum sample results for baseline, the relevant post-vaccination time points, and within the required time frames:
 - Baseline: Day 1 or within 60 days before study vaccine administration
 - Day 22: Day 19 through Day 25, inclusive

Analysis of demographic and baseline characteristics: The demographic and baseline characteristics will be summarized according to prior alphavirus vaccine exposure group and overall.

Age, height, weight, and body mass index at enrollment will be summarized by reporting the mean, standard deviation, median, minimum and maximum, and calculated by prior alphavirus vaccine exposure group and overall.

The frequencies and percentages of subjects by sex, race, and ethnicity will be presented by vaccine exposure group and overall. Demographic data will be tabulated for the Study, Immunogenicity Evaluable, and Safety populations.

9.5 Safety Analysis

Analysis of Extent of Exposure

The frequencies and percentages of subjects with vaccinations, and the timing of the vaccination, will be summarized by pre-exposure group for the Study Population.

All safety analyses will be based on the Safety Population.

9.5.1 Solicited AEs

With the exception of redness and swelling, all solicited AEs will be summarized according to severity grading scales defined in [Section 6.2](#) from “mild” to “potentially life-threatening.”

Solicited AEs will be recorded daily until 7 days post-injection using a structured memory aid. The analyses of solicited AEs (any event, after any injection, and after each injection) will be performed by maximum severity and by treatment group. In addition, solicited AEs ongoing after 7 days post-injection will also be recorded as unsolicited AEs.

Summary tables tallying the incidence, timing, duration and severity of any local or systemic solicited AE will be presented. The pre-exposure groups will be compared on the incidence of each type of solicited AE using pairwise Fisher’s exact tests. The percentage of subjects experiencing each solicited AE will also be presented by maximum severity.

The severity of redness and swelling recorded as diameters (mm) will be summarized according to categories based on the largest diameter linear measurement when the local reaction is present:

- Grade 0/absent = 0 to 24 mm.
- Grade 1/mild >24 to \leq 50 mm.
- Grade 2/moderate >50 to \leq 100 mm
- Grade 3/severe >100 mm or <100 mm with blister formation or skin breakdown

Events reported as not present (0 mm is entered) will be reported as Grade 0.

The following classifications are used in the summaries:

Grade 0 (0-24 mm), Any (>24-50 mm, >50-100 mm, >100 mm)

The following summaries of solicited events will be performed:

1. Solicited events by day post-injection, for each event and for any event.
2. Time of first onset of solicited adverse events, after injection, for each event and any event.
3. Solicited adverse events by maximum event severity, after injection, for each event and for any event.
4. Duration of solicited adverse events (defined as the number of total days during the post-vaccination collection period with the event), after injection, for each event and any event.
5. Solicited adverse events, occurrence of at least one event by category (local, systemic), after injection.

For each of the time points or time intervals presented in the summaries, only subjects with at least one observation (i.e., any non-missing values but excluding “Not done/unknown”) for the solicited adverse events will be summarized.

9.5.2 Unsolicited AEs

All the unsolicited AEs occurring during the study, will be recorded, regardless of their assessment of relatedness by the Investigator.

The original verbatim terms used by Investigators to identify AEs in the eCRFs will be mapped to preferred terms using the MedDRA dictionary. The unsolicited AEs will then be grouped by MedDRA preferred terms into frequency tables according to system organ class (SOC). All reported AEs, as well as AEs judged by the Investigator as at least possibly related to study vaccine, will be summarized by pre-exposure group, according to SOC and preferred term within SOC. When an unsolicited AE occurs more than once for a subject, the maximum severity and strongest relationship to the pre-exposure group will be counted.

Only treatment-emergent AEs will be summarized, i.e., excluding those after a subject has given informed consent, but before vaccination. The selection of unsolicited AEs and their assignment to time intervals will be done by day of onset and not by days ongoing/persisting.

Unsolicited AEs will be summarized by alphabetic SOC and preferred term as follows:

- Any unsolicited AE
- Possibly or probably related unsolicited AEs
- SAEs
- Possibly or probably related SAE
- Unsolicited AE leading to withdrawal
- Any AE leading to death

Listings of all AEs will be provided by subject.

Combined Solicited and Unsolicited Adverse Events

Solicited AEs continuing beyond 7 days after injection will be coded by MedDRA and combined with the unsolicited AEs. A summary of subjects with all combined solicited and unsolicited AEs, by SOC and preferred term, will be provided as well.

9.5.3 Analysis of Other Safety Data

The frequencies and percentages of concomitant medications will be tabulated overall and by treatment group. Medications will be coded using the WHODRUG dictionary.

9.6 Immunogenicity Analysis

All tests will be carried out at a 2-sided significance level of 0.05 and no adjustment for multiplicity will be applied.

Seroconversion Analysis:

The primary immunogenicity analysis will compare prior alphavirus vaccine recipients to alphavirus-naïve controls on the proportion in each group who seroconvert by anti-CHIKV neutralizing antibody at Day 22. Seroconversion is defined as a 4-fold or greater rise over baseline in anti-CHIKV neutralizing antibodies as assessed by a luciferase-based assay.

Specifically, we will test the hypotheses:

$$H_0: P_1 = P_2 \text{ vs. } H_1: P_1 \neq P_2$$

where P_1 and P_2 denote the proportion of subjects who seroconvert in the prior alphavirus vaccine recipients and the alphavirus-naïve controls, respectively.

The significance of the comparison of the pre-exposure groups will be assessed using a Fisher's exact test. The percentage who seroconvert in each group will be presented along with its 95% CI calculated using the Wilson method. A sensitivity analysis of the comparison will be performed using a logistic regression model that incorporates age, gender, and baseline titer as potential predictive factors. Fisher's test comparing seroconversion rates at other time points may also be performed. Similar analyses of the proportion who seroconvert will be conducted on Days 8, 29, 57 and 182 for anti-CHIKV neutralizing antibody and on Days 22 and 29 for total anti-CHIKV, total anti-VEEV and neutralizing anti-VEEV antibodies (secondary endpoints).

Threshold analyses:

The percentage of subjects achieving specified thresholds (e.g., ≥ 40 , 160, and 640 anti-CHIKV antibody titers), and associated Wilson 95% CIs, will also be calculated for Days 1, 8, 22, 29, 57 and 182 for neutralizing antibody and at Days 1, 22 and 29 for total anti-CHIKV, total anti-VEEV and neutralizing anti-VEEV antibodies (secondary end-points). The groups will be compared by pairwise Fisher's exact tests on the percentage achieving each threshold.

GMT analyses:

For the secondary comparisons based on GMT, the hypotheses tested will be

$$H_0: \mu_1 = \mu_2 \text{ vs. } H_1: \mu_1 \neq \mu_2$$

where μ_1 and μ_2 denote the GMT for the prior alphavirus vaccine recipients and the alphavirus-naïve controls, respectively.

The GMTs on Days 22 and 29 will be compared for differences between the pre-exposure groups. The GMTs and Geometric Mean Ratios (GMRs) will be analyzed via linear model. The primary model is an analysis of covariance (ANCOVA), with logarithmically-transformed titers (\log_{10}) as

the dependent variable and pre-exposure group, age, gender, as fixed effects and baseline log-transformed titer as the covariate in the model. The least square means estimated from the ANCOVA and their 95% CIs will be back-transformed and reported as the group GMT values. The GMR comparing the pre-exposure groups will be calculated by back-transforming the difference estimated from a linear contrast in the model. The 95% CI for the GMR will be calculated analogously.

The GMTs and GMRs based on antibody titers measured at all other protocol-specified time points will be analyzed as described above for Day 22. The difference in persistence of the antibody response induced after first vaccination at each time point will be visually assessed.

Summaries of both seroconversion and GMT will be presented by age and gender.

Exploratory endpoints (both categorical and continuous) for the heterologous alphavirus analyses will be analyzed descriptively.

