2.4.3 Secondary Immunogenicity Endpoints

- Anti-CHIKV neutralizing antibodies, determined by luciferase-based assay (NT₈₀), in prior alphavirus vaccine recipients versus alphavirus-naïve controls, assessed by
 - Geometric mean titer (GMT) and geometric mean ratio (GMR) on Days 1, 8, 22, 29, 57 and 182.
 - Seroconversion rates on Days 8, 29, 57 and 182.
 - The proportion of subjects with titers of at least 40, 160 or 640 on Days 1, 8, 22, 29, 57 and 182.
- Anti-CHIKV total antibodies, determined by immunoassay, in prior alphavirus vaccine recipients versus alphavirus-naïve controls, assessed by
 - GMT and GMR on Days 1, 22 and 29.
 - Seroconversion rate on Days 22 and 29, where seroconversion is a 4-fold rise in titer over baseline.
 - The proportion of subjects with titers of at least 40, 160 or 640 on Days 1, 22 and 29.
- Anti-VEEV total and neutralizing antibody, as determined by an immunoassay and a Plaque-Reduction Neutralization Test (PRNT₈₀) respectively, in prior alphavirus vaccine recipients versus alphavirus-naïve controls, assessed by
 - GMT and GMR on Days 1, 22 and 29.
 - Seroconversion rate on Days 22 and 29, where seroconversion is a 4-fold rise in titer over baseline.
 - The proportion of subjects with titers of at least 40, 160 or 640 on Days 1, 22 and 29.

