3.3. Data Handling Conventions and Transformations

By-subject listings will be presented for all enrolled subjects sorted by subject ID number, study arm, visit date, and time (if applicable). Data collected on log forms, such as AEs, will be presented in chronological order within subject.

Baseline is defined as the Day 1 value. If the Day 1 value is missing, then the last non-missing value prior to Day 1 will be used as the baseline value.

Data that are less than the limit of detection (LOD) or above the upper limit of assay reporting will be imputed as follows:

- Antibody titer assay results that are reported as less than the LOD will be imputed as the LOD/2 when calculating geometric mean titer (GMT) and geometric mean ratio (GMR). For example, if the LOD is 15 and a result is noted as “<15”, a titer of 15/2 (=7.5) will be imputed.
- For fold increase over baseline in antibody titer, if a value is < LOD, it will be imputed as the LOD. For example, if the LOD is 15 and a result is noted as “<15”, a titer of 15 will be imputed.
- A value that is one unit above the upper limit of assay reporting will be used for calculation of descriptive statistics if the datum is reported in the form of “> x” (where x is considered the limit of quantitation). Values with decimal points will follow the same logic as above.

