6.2.1. Analysis Methods for Secondary Immunogenicity Endpoints

The same method used for the primary immunogenicity analysis, excluding the estimated difference, will also be used for the secondary analysis of seroresponse rate, comparing the proportion of prior alpha subjects to the proportion of naïve alpha subjects having seroresponse by anti-CHIKV neutralizing antibodies on Days 8, 29, 57 and 182 and by anti-CHIKV total antibodies and anti-VEEV total and neutralizing antibodies on Days 22 and 29.

For the secondary analysis of GMT and GMR, the GMTs and GMRs at the specified time points will be compared for differences between the two study arms (prior alpha vs. naïve alpha) for each type of antibody listed above.

The primary model used for the immunogenicity evaluable population is an analysis of variance (ANOVA), with logarithmically-transformed (\log_{10}) titers as the dependent variable and study arm, age, and gender as the predictor variables in the model. The primary model used for the mITT population is the same except that \log_{10} baseline titer will be added as a predictor if there are subjects with measurable titers in the naïve alpha group at baseline. If any baseline titer is equal to zero, then one will be added to all baseline titers prior to taking the log. The least square means estimated from the ANOVA (or ANCOVA) and their 95% CIs will be back-transformed and reported as the group GMT values. The geometric mean ratio of the prior alpha group to the naïve alpha group, and its 95% CI, will be calculated by specifying a linear contrast between the groups in the model. Since the linear contrast yields a difference between groups in log-transformed space, the difference will be exponentiated to produce a geometric mean ratio of one group to the other. The p-value associated with each model comparison will also be reported. Additionally, the median, minimum and maximum will be summarized based on the non-transformed scale.

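### The protocol's GMT model adjusts the Day 1 titer for itself, so the Day 1 GMR is 1 by construction; under the SAP this survives only in the conditional mITT model for anti-CHIKV neutralizing antibody

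*Protocol*

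**What the plan says.** **Time points.** Protocol 2.4.3 lists "Geometric mean titer (GMT) and geometric mean ratio (GMR) on Days 1, 8, 22, 29, 57 and 182" for anti-CHIKV neutralizing antibody. For total anti-CHIKV and for total and neutralizing anti-VEEV antibody it lists "GMT and GMR on Days 1, 22 and 29". SAP 6.2 keeps Day 1 for all four measures.

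**Protocol model.** Section 9.6 takes log10 titer as "the dependent variable and pre-exposure group, age, gender, as fixed effects and baseline log-transformed titer as the covariate in the model". It then extends the method: "The GMTs and GMRs based on antibody titers measured at all other protocol-specified time points will be analyzed as described above for Day 22". No exception is made for Day 1.

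**Baseline.** SAP 3.3 states: "Baseline is defined as the Day 1 value". Protocol 9.4 allows a wider window ("Baseline: Day 1 or within 60 days before study vaccine administration"), but Appendix A schedules no antibody serum at screening, so in practice baseline is the Day 1 sample.

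**SAP model.** Section 6.2.1 differs from the protocol: "The primary model used for the immunogenicity evaluable population is an analysis of variance (ANOVA), with logarithmically-transformed" titers as outcome and study arm, age and gender as predictors, with no baseline term. In the mITT model, log10 baseline titer "will be added as a predictor if there are subjects with measurable titers" in the naïve arm at baseline. All secondary analyses are run on the IEP; only the anti-CHIKV neutralizing analysis is repeated on the mITT population. A p-value is reported for each model comparison.

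**IEP rule.** SAP 3.1.5 requires naïve subjects to be below the LOD at baseline for neutralizing antibody to CHIKV (LOD 15) and VEEV (LOD 20). SAP 3.3 replaces values below the LOD with LOD/2 for GMT and GMR.

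**The concern.** The Day 1 GMR shows whether prior recipients start with more antibody than controls. That bears on both questions in Protocol 1.3: whether earlier exposure changes the CHIKV response, and whether the vaccine boosts existing responses to other alphaviruses. A model that adjusts the Day 1 titer for the Day 1 titer cannot answer this. It reports equality for any data, with both arms given the same adjusted GMT. A Day 1 GMR of 1.00 in a table could be read as evidence that the arms were comparable at the start.

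In the SAP's mITT model the trigger also works the wrong way. The covariate enters only when some naïve Day 1 titers are measurable, that is, when the naïve arm varies and a two-sample comparison becomes possible. It then removes that comparison.

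**Working it through.** The documents state no value for the Day 1 GMR and no Day 1 titer distribution, so there is no plan figure to reproduce. The algebra needs no data. The numerical fits use assumed titers, 30 per arm, with age and gender in the model.

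**1. Protocol model at Day 1.** Let Y be log10 Day 1 titer and X be log10 baseline titer. The model is Y = a + b·arm + c·age + d·gender + e·X. At Day 1, X = Y. Least squares gives e = 1, a = b = c = d = 0 and residual sum of squares 0. Hence GMR = 10^b = 10^0 = 1, the two least-squares means coincide, and the estimated standard error is zero, so no valid CI exists.

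| Assumed Day 1 data | GMR without baseline (95% CI) | GMR with baseline | Adjusted GMT, both arms |
|---|---|---|---|
| VEEV-like: naïve all at 10, prior centered near 100 | 9.66 (6.14 to 15.19) | 1.000 | 31.1 |
| True GMR of 5, both arms varying | 4.84 (2.67 to 8.76) | 1.000 | 210.5 |
| CHIKV-like: 8 prior and 3 naïve measurable, rest at 7.5 | 1.30 (0.96 to 1.76) | 1.000 | 9.78 |

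With the covariate the slope was 1.0, the standard error of the arm coefficient was about 4e-15 or less, and the residual sum of squares was about 1e-26 or less. If every titer is below the LOD, X is collinear with the intercept (rank 4 of 5 columns).

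**2. Which planned Day 1 analyses are affected under the SAP.**

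| Day 1 analysis | Baseline covariate? | Consequence |
|---|---|---|
| IEP, total CHIKV and total VEEV | No | Estimable when titers vary |
| IEP, neutralizing CHIKV and VEEV | No | GMR not forced to 1; naïve arm constant (step 3) |
| mITT, neutralizing CHIKV, no naïve subject measurable | No | Naïve arm constant, as in the IEP |
| mITT, neutralizing CHIKV, any naïve subject measurable | Yes | GMR = 1 by construction |

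The SAP's instruction to add one to baseline titers if any is zero does not break the identity, because LOD/2 imputation leaves no zeros. The affected output is the Day 1 row of SAP Table 14.2.1.4.2.

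**3. The IEP naïve arm.** Every naïve neutralizing value is 15/2 = 7.5 for CHIKV and 20/2 = 10 for VEEV. With n per arm and prior-arm standard deviation s, and ignoring age and gender:

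- pooled variance = (s² + 0)/2 = s²/2
- SE of the difference = √(s²/2 × 2/n) = s/√n
- SE of the naïve mean = √(s²/2 × 1/n) = s/√(2n), although all naïve values are identical

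In the VEEV-like fit the SE of the arm difference was 0.0982, so the naïve SE is 0.0982/√2 = 0.0694. With 56 residual degrees of freedom (t about 2.003) the half-width is 0.139, and the naïve GMT of 10 receives a 95% CI of 10^(1 − 0.139) to 10^(1 + 0.139), about 7.3 to 13.8. All 30 values were exactly 10, and no titer can be recorded below 10. The unadjusted GMR also cannot fall below 1, because no prior value lies below LOD/2. Equality of the two means would require every prior recipient to be below the LOD as well, so a single measurable prior titer already settles the tested hypothesis.

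**The case against.** The strongest reply is that the SAP governs the analysis and has already dropped the covariate where it matters. All secondary analyses run on the IEP without it. The mITT repeat covers one antibody, and its trigger may never be met: natural alphavirus infection and prior chikungunya vaccination are excluded in both groups, and prior alphavirus vaccination in controls. If it is met, a fit with zero residual variance would be noticed. Day 1 differences also appear elsewhere: threshold percentages with Fisher tests for neutralizing antibody, medians and ranges, unadjusted CHIKV GMTs by race and gender, and individual listings.

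Most of this stands and sets the size of the point. A reader might infer from Protocol 9.6 that every Day 1 GMR in the trial will be reported as 1; SAP 6.2.1 does not support that. It does not remove the remaining case, since neither document exempts Day 1 and the SAP gives the rule that produces the empty result.

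On the IEP, it is fair to say that with equal arms the SE of the difference is about s/√n, which is real sampling variability among prior recipients. The comparison is then in effect prior recipients against the constant LOD/2. That is a reason to describe the prior arm directly; it does not justify the naïve CI or a two-sample p-value. Nor should a reader infer that the constant naïve arm forces the GMR to 1: it does not.

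**Conclusion.** The point holds in a limited form. Protocol 9.6, read as written, gives a Day 1 GMR of exactly 1 with no valid CI for every antibody. Under the SAP this is confined to one result, the Day 1 anti-CHIKV neutralizing GMR in the mITT population, and arises only if at least one naïve subject has a measurable baseline titer. The secondary point on IEP neutralizing titers concerns the naïve interval and the p-value, not the existence of a GMR.

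The algebra rests only on baseline being the Day 1 value. The size of what would be hidden depends on the actual titers; the ratios shown are assumptions. Total-antibody Day 1 GMRs under the SAP, all post-vaccination GMRs and the primary Day 22 Fisher comparison are unaffected, so nothing here questions the primary conclusion. It is worth correcting because the stated rule returns a fixed answer and the correction is very cheap.

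**What to change.** In Protocol 9.6 and SAP 6.2.1, state that baseline titer is a covariate for post-vaccination visits only. State that Day 1 is reported without it, as geometric mean with CI and percent at or above the LOD by arm. For IEP neutralizing titers at Day 1, report descriptively: the naïve arm as below the LOD by definition, the prior arm with its own geometric mean and CI, and no between-arm p-value. The same treatment suits the mITT Day 1 row when no naïve subject is measurable. While editing, record the move from ANCOVA to ANOVA for the IEP in SAP Section 8, which does not list it.

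The cost is one or two sentences in each document and a change to the Day 1 rows of the GMT tables. No extra data, samples or subjects are needed.
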